#### **Randomized Crossover Trial**

Eligible participants will be randomly assigned to one of two treatment groups for 13 weeks each:

- 1. Group A: study system for period 1 for 13 weeks, then SAP for period 2 for 13 weeks
- 2. Group B: SAP for period 1 for 13 weeks, then study system for Period 2 for 13 weeks

Study System Period: The participant will be trained regarding AID study system use including meal announcement, meal bolusing, correction doses, and exercise. Participants will be expected to use the study system at all times at home with the exception of times of illness.

SAP Period: During the SAP period, participants will use their own insulin pump and a study-provided Dexcom G6 sensor.

• PLGS mode on the pump can be used if feasible but an AID system cannot be used.

#### **Study Flow**

Period 1 will commence on the day of randomization with initiation of the study system or continued use of personal pump SAP.

Both groups will have the same contact and visit schedule in both period 1 and period 2

- Visits at 2 weeks, 6 weeks, and 13 weeks
- Phone contacts at 3 days, 4 weeks, and 9 weeks

At randomization, and at each end of period visit, central lab HbA1c measurement will be made, a pregnancy test will be performed in applicable subjects, and quality of life and treatment satisfaction questionnaires will be completed.

At the end of period 1 visit, the intervention will be switched to the study system or SAP for period 2. There will not be a washout period.

Throughout the study, the occurrence of adverse events and device issues will be solicited and recorded.

37 38

The following table provides an overview of the schedule of study visits, phone contacts, and key procedures.

## **Table 2: Schedule of Visits and Procedures**

42 43

44 45 46

47

48

49

50

	Screening Visit	CGM Run-in Visit	Randomization Visit	Days (d) or Weeks (w) from the Start of Each of Two 13-Week Study Periods 						
				$0d^2$	3d	2w	4w	6w	9w	13w
Visit (V) or Contact (C)			v	V	C	V	C	V	C	V
Informed Consent	X									
Eligibility Assessment	X									
Medical history/ physical exam	X									
Height, weight, blood pressure and pulse	X									X
HbAlc (POC or local lab, if needed)	X									
HbA1c (Central lab)			X							X
C-peptide and blood glucose (Central Lab)			X							
Pregnancy test (females of child-bearing potential)	X		X	X 						
Questionnaires	X									X
Assessment of CGM use	X	X								
Study system training			X	X 						
AE Assessment		X	X		X	X	X	X	X	X
Upload device data from home					X		X		X	
Download device data at clinic visit		X				X		X		X

1. Two 13-Week treatment periods with no intervening washout

2. Will coincide with Randomization Visit for study period 1

3. For study period 2 only

4. For Group B participants (those assigned to use SAP during period 1) only

## 2. Comparison with Protocol

51 52 53

The author ([name]) attests the consistency between this document and Protocol v4.1.

54

The following analyses were added here that are not in the protocol:

55 56

57

58 59

60

61

62

63

64

65

- Binary CGM outcomes:
  - $\circ$  % in range 70-180 mg/dL >70%
  - $\circ$  % < 54 mg/dL < 1%
  - $\circ$  % in range 70-180 mg/dL >70% and % <54 mg/dL <1%
- Sensitivity Analyses First Week of CGM data
- Additional Tabulations and Analyses weekly CGM metrics during MPC period
- Hypoglycemia events (defined as at least 15 consecutive minutes <54 mg/dL) was moved from safety to secondary outcomes and replaced the previous hypoglycemia events (defined as at least 15 consecutive minutes < 70 mg/dL)
- CGM-measured hyperglycemic events ( $\geq$ 15 minutes with glucose concentration  $\geq$ 300 mg/dL) moved from safety to secondary outcomes.

66 67

68 69

## 3. Statistical Hypotheses

70 71

72

73

74

The primary outcome for this study is CGM-measured % in range 70-180 mg/dL over 12 weeks in each one of the two crossover periods. The intervention will be considered effective if % time in range during the MPC period is superior to the SAP period using a statistical significance of  $\alpha$ =0.05 and the model specified below in Section 7 (i.e. p < 0.05)

75 76

The null/alternative hypotheses are:

77 78 a. Null Hypothesis: There is no difference in mean CGM-measured % in range 70-180 mg/dL over 12 weeks between SAP and MPC periods

79 80 b. Alternative Hypothesis: The mean CGM-measured % in range 70-180 mg/dL over 12 weeks is different for SAP and MPC periods.

81 82

# 4. Sample Size

83 84

85

86

87

88

89

Sample size has been computed for the primary outcome (CGM-measured % in range 70-180 mg/dL). Data from the SAP group in DCLP3 (The International Diabetes Closed Loop Protocol 3 Pivotal Trial of t:slim X2 with Control-IQ Technology) were used to calculate sample size specific to ≥18 years age group. For the SAP group, the standard deviation for time in range 70-180 mg/dL over the course of the first 3 months was 12% (95% CI 10% to 16%) and the correlation between the first 3 months and last 3 months was 0.92.

- 90
- A total sample size was computed to be N=31 for the following assumptions: (1) two 3-month periods 91 [MPC:SAP] crossover randomization, (2) 90% power, (3) a 8% absolute increase in % time in range 70-
- 180 mg/dL, (4) a SD of 17%, (5) a correlation between the two periods of 0.70, and (6) 2-sided type 1 92
- 93 error of 0.05.

The total sample size has been increased to N=35 to account for potential dropouts. 94 95 5. Outcome Measures 96 97 98 **5.1. Primary Efficacy Endpoint:** • CGM-measured % in range 70-180 mg/dL over 12 weeks in each one of the two crossover 99 periods 100 101 102 5.2. Secondary Efficacy Endpoints 103 104 5.2.1. Hierarchical Endpoint The following secondary endpoint will be tested in a hierarchical fashion only if the primary efficacy 105 endpoint reached statistical significance as described in Section 8.1 below: 106 • CGM-measured % below 54 mg/dL over 12 weeks in each one of the two crossover periods 107 108 (non-inferiority outcome with a non-inferiority limit of 1.0%). This is the only non-inferiority and one-sided outcome in the study. 109 110 **5.2.2. Other Secondary Endpoints** 111 The following endpoints are considered secondary. 112 • CGM metrics related to overall control over 12 weeks 113 o % in range 70-140 mg/dL 114 o mean glucose 115 o glucose variability measured with the coefficient of variation 116 o glucose variability measured with the standard deviation 117  $\circ$  % in range 70-180 mg/dL >70% 118  $\circ$  % in range 70-180 mg/dL >70% and % <54 mg/dL <1% 119 • CGM metrics related to hypoglycemia over 12 weeks 120  $\circ$  % < 70 mg/dL 121  $\circ$  % < 60 mg/dL 122 o % <54 mg/dL (superiority – see details in Section 5.2.1 above) 123 o low blood glucose index 124 o hypoglycemia events (defined as at least 15 consecutive minutes <54 mg/dL) 125  $\circ$  % < 54 mg/dL < 1% 126 • CGM metrics related to hyperglycemia over 12 weeks 127  $\circ$  %>180 mg/dL 128  $\circ$  % >250 mg/dL 129  $\circ$  % > 300 mg/dL 130 o high blood glucose index 131 o CGM-measured hyperglycemic events (≥15 minutes with glucose concentration >300 132 133 mg/dL) • CGM metrics by time of day 134

Daytime only (06:00AM to 00:00AM)

o Calculate all CGM metrics listed above (including the primary outcome) for:

All 24 hours of the day (the primary outcome is over 24hr)

135

136

138 139 140 141	
 
Nighttime only (00:00AM to 06:00AM)
 
HbA1c at 13 weeks
 
HbA1c
 
HbA1c
 

142 143 144	
 
HbA1c <7.5%
 
Insulin at 13 weeks
 
Total daily insulin (units/kg)
 

145 146	
 
Basal: bolus insulin ratio
 
Weight and body mass index at 13 weeks
 

147	
 
Diabetes Distress Scale at 13 weeks – total score and 4 subscales:
 

148 149 150 151	
 
Emotional burden
 
Physician-related distress
 
Regimen-related distress
 
Interpersonal distress
 

152	• Glucose Monitoring Satisfaction Survey – measures treatment satisfaction and burden
153	Hypoglycemia Confidence Scale
154	Diabetes Technology Attitudes survey
155	
 
INSPIRE survey scores - MPC period only
 

156	
 
System Usability Survey - MPC period and at 13 weeks only
 

157 158 159 160 161 162 163 164 165 166 167 168 169	
 
5.3 Calculation of CGM Metrics (primary and secondary):
 
Baseline: The last 2 weeks of personal CGM data or last 2 weeks of CGM run-in data will serve as baseline. If a participant has <72hr of data in the last two weeks of CGM run-in, then would go back to the 3rd week and, if still <72hr, then would repeat and go back to the 4th week.
 
Each one of the Two Follow-up Periods: Since participants will receive up to 7 days of training before taking the MPC system home, the first 7 days in the SAP and MPC periods will not be included in the CGM analyses. CGM data starting from day 8 following randomization visit through the 13-week visit for first period and from day 8 following treatment reassignment through the second 13-week visit for the second crossover period will be included in the calculation of CGM metrics.
 
At least 72hr of CGM data at baseline and in each one of the two periods are needed for the
 

170	metrics to be calculated.
171 172 173	
 
All CGM metrics at baseline and follow-up will be calculated giving equal weight to each sensor reading for each participant.
 

174	5.4. Questionnaires
175 176 177	All questionnaires will be administered online, and participants are allowed to skip specific questionnaires or items within a questionnaire. The data might therefore include some missing items. All questionnaires will be scored according to the instructions given in the manual. In case no manual exists

- for a given questionnaire or the manual does not provide guidance on how to handle missing items, then
- the following criteria will be applied.
- At least 75% of the questions must be completed to be included in the analysis. This 75% rule will be
- applied separately for the total score and each subscale so it is possible the sample size will be different
- for some subscales. The score used for analysis will be based on the average among the questions that
- were answered and then scaled accordingly.

184 185

186

187

188 189

190

### **5.5 Analysis Windows**

Analysis windows apply to the following outcomes measured at 13-week visit in each one of the two crossover periods:

- HbA1c
- Insulin metrics
- Height/Weight
- Questionnaires

191192193

194

In order to be included in the corresponding analyses, these data must be collected between days 76 and 106 for both the first and second 13-week visit date within each period. The target date is 91 days from the beginning of each one of the two crossover periods.

195 196 197

This does not apply to the CGM metrics which are calculated as described above.

198 199

## 6. Description of Statistical Methods

200201202

203

204205

206

207

208

209

210

211

212

213

214

215

216

217

218

### 6.1. General Approach:

- All analyses comparing the MPC with the SAP period will follow the intention-to-treat (ITT) principle with each participant analyzed according to the treatment period assigned by randomization.
- In the unlikely event that a randomized participant is later found to be ineligible, the participant will be excluded from all analyses.
- Otherwise, all randomized participants with at least 72h of CGM data in at least 1 follow-up period will be included in the primary and secondary analyses.
- All p-values apart from the secondary hierarchical CGM-measured % below 54 mg/dL- will be two-sided.
- Standard residual diagnostics, based on the differences between the two periods, will be performed for all analyses. If values are highly skewed, then a winsorizing at 10/90th percentile, nonparametric, or MM estimation methods will be used instead for the primary and secondary outcomes. Previous experience suggests that no transformation, nonparametric, or MM estimation analyses will be necessary for % time in range 70-180 mg/dL, % above 180 mg/dL, mean glucose, or HbA1c. Other outcomes like % below 54 mg/dL are skewed; however, the differences between the two periods may follow a normal distribution and there may be no need for transformation, nonparametric, or MM estimation.

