
300 6) Participation in another pharmaceutical or device trial at the time of enrollment or during301 the study

302 **2.3 Screening Procedures**

303 After informed consent has been signed, a potential participant will be evaluated for study

eligibility through the elicitation of a medical history, performance of a physical examination
 by study personnel, and local laboratory testing if needed to screen for exclusionary medical
 conditions.

307 Individuals who do not initially meet study eligibility requirements may be rescreened at a later 308 date per investigator discretion. Individuals who do meet eligibility criteria will proceed to the 309 Pilot Phase, CGM Run-In period, or Crossover Trial (as applicable, see below), which will be 310 autocated to start on the same day as generating, or up to 14 days thereafter

310 expected to start on the same day as screening, or up to 14 days thereafter.

311 **2.3.1 Data Collection and Testing**

- 312 A standard physical exam (including vital signs and height and weight measurements) will be
- 313 performed by the study investigator or qualified designee (e.g. a physician, fellow, nurse
- 314 practitioner, or a physician assistant).
- The following procedures will be performed/data collected/eligibility criteria checked and documented:
- Inclusion and exclusion criteria assessed
- Demographics (socioeconomic status, date of birth, sex, race, and ethnicity)
- Contact information (retained at the site and not entered into study database)
- Medical history
- Diabetes history
- Concomitant medications
- Physical examination to include:
- → Weight, height

- Vital signs including measurement of blood pressure and pulse
- Blood draw or fingerstick for HbA1c level measured using the DCA Vantage or similar point-of-care device or local lab, if measurement not available from past 3 months
- Urine pregnancy test for all females of child-bearing potential
- The following questionnaires will be administered:
- Diabetes Distress Scale
- Glucose Monitoring Satisfaction Survey
- Hypoglycemia Confidence
- Diabetes Technology Attitudes
- → INSPIRE Survey

335 Screening procedures may last approximately 1-2 hours.

336 **2.3.2 Screen Failures**

- 337 Individuals who do not initially meet study eligibility requirements may be rescreened at a later
- 338 date per investigator discretion.

Chapter 3: Pilot Phase

341 **3.1 Description**

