432

- 438 The randomization visit is expected to begin on the same day the CGM Run-In period is
- 439 completed (or it can be on the same day of screening if the run-in phase is skipped). If not on the
- same day, the randomization visit should occur within 14 days of the end of the run-in phase (or
- 441 screening visit if run-in skipped).
- 442 Participants in the Pilot Phase will be on hold until the safety assessment of the Pilot Phase has
- been completed and the RCT begins. Once the RCT is initiated, Pilot Phase participants who
- 444 will participate in the RCT will complete the consent process for the RCT and will then be able
- 445 to complete the randomization visit.
- 446 If it has been more than 30 days since the Screening visit, changes in medications and medical
- 447 conditions since screening will be solicited, and if necessary the standard physical exam
- 448 described in section 2.3 will be repeated.
- Eligibility criteria from screening will be reviewed again (if not the same day) to verify
- 450 eligibility, and the study staff will evaluate whether the participant can safely use the study
- 451 system. If the participant is no longer eligible based on these criteria, the participant will be
- 452 dropped from the study.

453 **5.2 Data Collection and Testing**

- 454 The following procedures will be done at the randomization visit:
- Blood sample to send to the central laboratory for HbA1c; random, non-fasting C-peptide;
 and glucose
- Urine pregnancy test for all females of child-bearing potential (if not performed within the prior 6 days)

459 **5.3 Randomization**

- 460 Eligible participants will be randomly assigned, stratified by site, to one of two groups to461 determine treatment order during the 26-week study:
- 462 1. Group A: study system for period 1 for 13 weeks, then SAP for period 2 for 13 weeks
- 463 2. Group B: SAP for period 1 for 13 weeks, then study system for Period 2 for 13 weeks
- 464 Participant randomization assignment is determined after the Randomization Visit data are
- 465 entered on the study website. The data from this visit and where applicable, prior visits, are
- 466 assessed to verify eligibility prior to the randomization process being completed.

467 5.4 Device Training and Study Supplies

468 5.4.1 CGM System Training, Initiation, and Supplies

- 469 Participants who were eligible to skip the CGM Run-In phase will have the study CGM initiated

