12.4.3 CGM Metrics Calculations
The last 2 weeks of personal CGM data or last 2 weeks of CGM run-in data will serve a baseline. Since participants will receive up to 7 days of training before taking the CLC

baseline. Since participants will receive up to 7 days of training before taking the CLC system
home, the first 7 days in the SAP and CLC periods will not be included in the CGM analyses.
CGM data starting from day 8 following randomization visit through the 13-week visit for first
period and from day 8 following treatment reassignment through the second 13-week visit for the
second crossover period will be included in the calculation of CGM metrics. At least 72hr of
CGM data at baseline and in each one of the two periods are needed in order for the metrics to be
calculated.

1210 12.5 Analysis Datasets and Sensitivity Analyses

1211 All analyses comparing the CLC period with SAP period will follow the intention-to-treat (ITT)

- 1212 principle with each period and participant analyzed according to the randomization. All
- randomized periods with at least 72hr of CGM data will be included in the primary and secondary hierarchical analyses.
- 1215 Safety outcomes will be reported for all enrolled participants, irrespective of whether the
- 1216 participant was randomized or the study was completed.

1217 **12.5.1 Per Protocol Analyses**

- If more than 10% of participants in a treatment period have fewer than 168 hours of CGM data, the primary analysis will be replicated excluding such subjects.
- The primary analysis will be replicated only with participants who used the system in CL mode for >80% during the CLC period and used the sensor for >80% during the SAP period.

as

1223 12.5.2 Sensitivity Analyses

1224 **12.5.2.1 Missing Data**

1225 It is worth emphasizing that any statistical method for handling missing data makes a number of 1226 untestable assumptions. The goal will be to minimize the amount of missing data in this study so 1227 that results and conclusions will not be sensitive to which statistical method is used. To that end, 1228 sensitivity analyses will be performed to explore whether results are similar for primary analysis 1229 when using different methods. The following methods will be applied:

- Available cases only (≥72hr in at least one of the two cross-over periods, primary analysis described below)
- Rubin's multiple imputation

1233 **12.5.2.2 Carry-over Effect**

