### **6.2 Analysis Cohorts**

222223

- 224 Primary and Secondary Analyses:
- All randomized participants and periods will be analyzed according to the ITT principle as described above.
- All participants with at least 72hr of CGM data in at least one randomized period will be included in the CGM-based analyses.
- All randomized periods with a HbA1c measurement at 13 weeks will be included in HbA1c analyses. Similar approaches will be followed for the other secondary outcomes like insulin, weight/BMI, and questionnaires analyses.

232

233

235

236

237

238

239

- Per Protocol (PP) Analyses:
- Three different per protocol analyses will be considered:
  - If more than 10% of participants have fewer than 168 hours CGM data in either treatment period, the primary and secondary hierarchical analyses will be replicated excluding such participants.
  - The primary and secondary hierarchical analyses will be replicated restricting to participants who:
    - ➤ used the system in CL mode for >80% (i.e. >1,613 hours) during the MPC period, and
    - ➤ used the sensor for >80% (i.e. >1,613 hours) during the SAP period.

240241

- 242 Safety Analyses:
  - Safety outcomes will be reported for all randomized participants by period. Separately, any reported adverse events pre-randomization will be tabulated.

245

246

243

244

- Sensitivity Analysis:
- Missing Data: As noted below in Section 6.2, all participants with ≥72hr of CGM data in at least one of the two crossover periods will be included in primary analyses. It is also worth emphasizing that any statistical method for handling missing data makes untestable assumptions. The goal will be to minimize the amount of missing data in this study so that results and conclusions will not be sensitive to which statistical method is used. To that end, sensitivity analyses will be performed to explore whether results are similar for primary and secondary hierarchical analysis when using different methods. The following methods will be applied:
  - Available cases participants with ≥72hr of CGM data in at least one of the two crossover periods (this is the default method)
  - o Complete cases only participants with ≥72hr of CGM data in both crossover periods
  - o Rubin's multiple imputation

257258

254

255

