## 9. Safety Analyses

378379

385

386

387

- All enrolled participants will be included in these analyses and all their safety events up to the second and final 13-week visit will be reported.
- The circumstances of all reportable cases of the following will be summarized and tabulated by treatment period:
- Severe hypoglycemia
  - Diabetic ketoacidosis
  - Ketone events defined as day with ketone level  $\geq 1.5$  mmol/L
  - Worsening of HbA1c from start of the period to 13 weeks by >0.5%
- Other serious adverse events (SAE) and serious adverse device events (SADE)
- Adverse device effects (ADE)
  - Unanticipated adverse device effects (UADE)
- 391 Statistical analyses to compare rates of severe hypoglycemia and rates of diabetic ketoacidosis between
- treatment arms will only be performed if there are at least 10 events after randomization. If yes, the
- numbers will be compared between the two treatment periods using a robust Poisson regression. The
- amount of follow up will be included as an offset covariate to compare the rates.
- Comparison of safety outcomes between the two treatment periods only include those events occurring
- on or after randomization until the final 13-week visit.
- The analyses for the two continuous CGM-measured outcomes will parallel those mentioned above for
- 398 the primary outcome.

399 400	The CGM metrics listed in the above efficacy section 5.2.2. also serve as safety measures if there is worsening in the intervention group.
401 402	Any pre-randomization adverse events will be tabulated separately and will include participants who were never randomized.
403	
404 405	10. Device Issues
406 407	Reported device malfunctions or other issues for each type of study device (e.g., closed loop system, CGM, blood glucose meter)
408 409 410	11. Protocol Adherence and Retention
411 412	The following tabulations and analyses will be performed by treatment period to assess protocol adherence for the study:
413 414	
 
Number of protocol and procedural deviations per participant along with the number and percentage of participants with each number of deviations
 

415	
 
Number of protocol and procedural deviations by severity with brief descriptions listed
 

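### SAP 6.1 drops randomized participants later found ineligible from every analysis, an exclusion the protocol's analysis set does not contain

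*SAP*

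**What the plan says.** Here SAP means the statistical analysis plan; the comparator is called the control period.

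- **SAP 6.1**, second bullet, directly after the intention-to-treat commitment: "In the unlikely event that a randomized participant is later found to be ineligible, the participant will be excluded from all analyses". The next bullet admits the remaining randomized participants with 72 hours of CGM data in at least one period.
- **Protocol 12.5** sets the efficacy set by intention-to-treat; all "randomized periods with at least 72hr of CGM data will be included in the primary and secondary hierarchical analyses". It has no ineligibility exception. The opening of protocol Chapter 5 adds that anyone randomized is counted whether or not the assigned treatment is received.
- **SAP 2**: the author "attests the consistency between this document and Protocol v4.1". The list that follows covers added analyses and moved or redefined outcomes. This exclusion is not in it.
- **Safety.** Protocol 12.5: "Safety outcomes will be reported for all enrolled participants, irrespective of whether the" person was randomized or finished. SAP 6.2: "Safety outcomes will be reported for all randomized participants by period". SAP 9: "All enrolled participants will be included in these analyses and all their safety events up to the second" and final 13-week visit.
- **Eligibility.** Protocol 5.3 has the visit data "assessed to verify eligibility prior to the randomization process being completed". Exclusion criterion 6 in protocol 2.2.2 reads "Participation in another pharmaceutical or device trial at the time of enrollment or during" the study.

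**The concern.** Removing randomized participants is defensible only when the reason was fixed before randomization and the decision cannot be influenced by assignment or outcome. SAP 6.1 requires neither, and it names no decision maker. Participants and staff know which system is in use. Under protocol 6.2.9, staff look at study-system data at least weekly. Criterion 6 can be failed after randomization. Inclusion criterion 10 and exclusion criterion 5 rest on investigator judgement, which nothing stops from being revisited once follow-up is under way.

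What is at stake for efficacy is a possible selection bias in the primary comparison and in the non-inferiority test for time below 54 mg/dL, which the protocol's own analysis set does not have. For safety, the literal rule would tabulate events in people who were never randomized (SAP 9) while omitting events in a treated participant later judged ineligible.

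**Working it through.** **1. The texts side by side**

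| Question | Protocol | SAP 6.1 | SAP elsewhere |
|---|---|---|---|
| Efficacy set | All randomized periods with 72 h of CGM data (12.5) | Same, minus those later found ineligible | 6.2: all randomized, referring back to 6.1 |
| Safety set | All enrolled (12.5, 12.8) | Ineligible removed from all analyses | 6.2: all randomized; 9: all enrolled |
| Timing limit on the rule | No such rule | None | None |
| Masked decision | No such rule | None | Only for subgroup cutpoints (15) |
| Declared as a change | – | – | Not in section 2 |

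**2. Reproducing the planned sample size** (protocol 12.3, SAP 4: SD 17, correlation 0.70, effect 8 points, 90% power, two-sided 0.05)

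- SD of the within-person difference = 17 × √(2 × (1 − 0.70)) = 13.17.
- Normal approximation: ((1.96 + 1.2816) × 13.17 / 8)² = 28.5, so 29.
- Paired t test (noncentral t): N = 31, power 90.5%. The stated N of 31 is reproduced.

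**3. Power when participants are lost** (same paired t test, complete pairs)

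| n | 35 | 34 | 33 | 32 | 31 | 30 | 29 |
|---|---|---|---|---|---|---|---|
| Power | 93.7% | 93.0% | 92.3% | 91.4% | 90.5% | 89.5% | 88.4% |

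From 35 complete pairs, three exclusions leave 91.4%. From the planned minimum of 32 completers, three leave 88.4%.

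**4. Possible shift in the estimate**

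The number excluded (1, 2 or 3 of 35) is an assumption. I simulated 200,000 samples of 35 normal differences and took the mean of those kept minus the mean of all 35. Two SDs of the difference were used: the planning value, 13.17, and the value implied by the earlier trial's control group (SD 12, correlation 0.92), 12 × √(2 × (1 − 0.92)) = 4.80. The second leaves out variation in treatment effect, so it is a low value.

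| Who is removed | SD of difference | 1 | 2 | 3 |
|---|---|---|---|---|
| Unrelated to outcome | either | 0 | 0 | 0 |
| At random from the lowest 9 of 35 | 13.17 | 0.47 | 0.98 | 1.51 |
| Exactly the lowest (upper bound) | 13.17 | 0.82 | 1.52 | 2.16 |
| At random from the lowest 9 of 35 | 4.80 | 0.17 | 0.36 | 0.55 |
| Exactly the lowest (upper bound) | 4.80 | 0.30 | 0.55 | 0.79 |

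Entries are percentage points of time in range, towards the study system. Hand check of one cell: the smallest of 35 standard normal values averages about −2.11, so removing it shifts the mean by 13.17 × 2.11 / 34 = 0.82.

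**5. False superiority at the upper bound**

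With no true effect, the chance of declaring the study system superior should be 2.5%. Removing exactly the lowest 1, 2 or 3 raises it to about 6%, 12% and 20%. The t statistic does not depend on scale, so these rates are the same for either SD. Random removal leaves it at 2.5%.

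The paired t test is simpler than the planned repeated-measures model with baseline as a third observation. The documents give no SD for time below 54 mg/dL, so no figure is offered for the non-inferiority test.

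**The case against.** The most natural reading of the sentence is that someone turns out not to have qualified at entry. Eligibility is checked before assignment, the SAP itself calls the event unlikely, and later problems such as pregnancy or unsafe device use have their own discontinuation rules, none of which removes data. In a crossover, both periods of a person leave together, so the rule cannot thin out one treatment; bias needs selection on the within-person difference and an arguable eligibility failure in that same person. For efficacy the SAP is clear about precedence: the bullet after the rule treats it as an exception, and 6.2 refers back. The section 2 list is headed as added analyses, and protocol 12.1 leaves detail to the SAP. Adding timing and masking conditions to the sentence would close the bias route without deleting it.

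Much of this stands as a limit on size: the event is rare, harm requires outcome-related selection, and 6.1 and 6.2 do not conflict on efficacy. It does not remove the point. A deliberate exception is still a departure from protocol 12.5. The section 2 list also records moved and redefined outcomes, so it works as a change log. The wording of criterion 6 and the judgement-based criteria keep post-randomization decisions open. Losing both periods together does not protect the within-person difference, which is the quantity being estimated. The safety contradiction needs no argument about bias.

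**Conclusion.** The concern holds. SAP 6.1 adds an undeclared, unrestricted and unmasked exclusion to an analysis set that the protocol defines without one, and it conflicts with three statements of the safety population. The text conflict is certain. The bias is only possible: zero if exclusions are unrelated to outcome and, for 1 to 3 exclusions at the planning SD, at most about 0.8 to 2.2 points on average under the worst selection, against a planned effect of 8. Those figures rest on an assumed number of exclusions, normal differences and 35 complete pairs; they are bounds, not predictions. Power is a minor matter. For safety, the more specific sections would probably prevail, so the practical risk is inconsistent reporting. The front pages are not available, so it is assumed that the protocol supplied is v4.1. This should be corrected before the data are tabulated by treatment.

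**What to change.** - Delete the exclusion sentence from SAP 6.1.
- State that all randomized participants enter the primary and hierarchical analyses, subject only to the 72-hour CGM rule, as in protocol 12.5.
- State that the safety tables include participants later found ineligible, and align SAP 6.2 and SAP 9 with protocol 12.5 on randomized versus enrolled.
- Add a sensitivity or per-protocol analysis that leaves out ineligible participants, limited to criteria already violated before randomization, with a named decision maker who has not seen follow-up CGM data.

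The cost is one deleted sentence, a few clarifying ones and one extra analysis. No planned figure changes. The downside is that a wrongly enrolled participant stays in the primary estimate; the sensitivity analysis shows how much that matters.
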